#### 4.2.4 Methods for Evaluation of Measurable Disease

All measurements should be taken and recorded in metric notation using a ruler or calipers. All baseline evaluations should be performed as closely as possible to the beginning of treatment and never more than 4 weeks before the beginning of the treatment.

The same method of assessment and the same technique should be used to characterize each identified and reported lesion at baseline and during follow-up. Imaging-based evaluation is preferred to evaluation by clinical examination unless the lesion(s) being followed cannot be imaged but are assessable by clinical exam.

- Clinical lesions: Clinical lesions will only be considered measurable when they are superficial (e.g., skin nodules and palpable lymph nodes) and ≥10 mm diameter as assessed using calipers (e.g., skin nodules). In the case of skin lesions, documentation by color photography, including a ruler to estimate the size of the lesion, is recommended.
- Chest x-ray: Lesions on chest x-ray are acceptable as measurable lesions when they are clearly defined and surrounded by aerated lung. However, CT is preferable.
- Conventional CT and MRI: This guideline has defined measurability of lesions on CT scan based on the assumption that CT slice thickness is 5 mm or less. If CT scans have slice thickness greater than 5 mm, the minimum size for a measurable lesion should be twice the slice thickness. MRI is also acceptable in certain situations (e.g., for body scans). Use of MRI remains a complex issue. MRI has excellent contrast, spatial, and temporal resolution; however, there are many image acquisition variables involved in MRI that greatly impact image quality, lesion conspicuity, and measurement. Furthermore, the availability of MRI is variable globally. As with CT, if an MRI is performed, the technical specifications of the scanning sequences used should be optimized for the evaluation of the type and site of disease. Furthermore, as with CT, the modality used at follow-up should be the same as was used at baseline and the lesions should be measured/assessed on the same pulse sequence. It is beyond the scope of the RECIST guidelines to prescribe specific MRI pulse seguence parameters for all scanners, body parts, and diseases. Ideally, the same type of scanner should be used and the image acquisition protocol should be followed as closely as possible to prior scans. Body scans should be performed with breath-hold scanning techniques, if possible.

## 4.2.5 Response Criteria

## 4.2.5.1 Evaluation of Target Lesions

- Complete Response (CR): Disappearance of all target lesions. Any pathological lymph nodes (whether target or non-target) must have reduction in short axis to <10 mm.

- Partial Response (PR): At least a 30% decrease in the sum of the diameters of target lesions, taking as reference the baseline sum diameters.
- Progressive Disease (PD): At least a 20% increase in the sum of the diameters of target lesions, taking as reference the smallest sum on study (this includes the baseline sum if that is the smallest on study). In addition to the relative increase of 20%, the sum must also demonstrate an absolute increase of at least 5 mm. (Note: the appearance of one or more new lesions is also considered progressions).
- Stable Disease (SD): Neither sufficient shrinkage to qualify for PR nor sufficient increase to qualify for PD, taking as reference the smallest sum diameters while on study.

# 4.2.5.2 Evaluation of Non-Target Lesions

- Complete Response (CR): Disappearance of all non-target lesions and normalization of tumor marker level. All lymph nodes must be nonpathological in size (<10 mm short axis). Note: If tumor markers are initially above the upper normal limit, they must normalize for a patient to be considered in complete clinical response.
- Non-CR/Non-PD: Persistence of one or more non-target lesion(s) and/or maintenance of tumor marker level above the normal limits.
- Progressive Disease (PD): Appearance of one or more new lesions and/or unequivocal progression of existing non-target lesions. Unequivocal progression should not normally trump target lesion status. It must be representative of overall disease status change, not a single lesion increase.
- Although a clear progression of "non-target" lesions only is exceptional, the
  opinion of the treating physician should prevail in such circumstances, and
  the progression status should be confirmed at a later time by the review
  panel (or Principal Investigator).

### 4.2.5.3 Evaluation of Best Overall Response

The best overall response is the best response recorded from the start of the treatment until disease progression/recurrence (taking as reference for progressive disease the smallest measurements recorded since the treatment started). The patient's best response assignment will depend on the achievement of both measurement and confirmation criteria.

**Table 2. For Patients with Measurable Disease (i.e., Target Disease)** 

Target Lesions	Non-Target Lesions	New Lesions	Overall Response	Best Overall Response when Confirmation is Required*
CR	CR	No	CR	≥4 wks. Confirmation**
CR	Non-CR/Non-PD	No	PR	
CR	Not evaluated	No	PR	>4 wks. Confirmation**
PR	Non-CR/Non-PD/not evaluated	No	PR	24 WKS. Committation
SD	Non-CR/Non-PD/not evaluated	No	SD	Documented at least once > 4 wks. from baseline**
PD	Any	Yes or No	PD	
Any	PD***	Yes or No	PD	no prior SD, PR or CR
Any	Any	Yes	PD	

\*See RECIST 1.1 manuscript for further details on what is evidence of a new lesion.

**Note:** Patients with a global deterioration of health status requiring discontinuation of treatment without objective evidence of disease progression at that time should be reported as "symptomatic deterioration." Every effort should be made to document the objective progression even after discontinuation of treatment.

Table 3. For Patients with Non-Measurable Disease (i.e., Non-Target Disease)

Non-Target Lesions	New Lesions	Overall Response	
CR	No	CR	
Non-CR/non-PD	No	Non-CR/non-PD*	
Not all evaluated	No	not evaluated	
Unequivocal PD	Yes or No	PD	
Any	Yes	PD	

\* 'Non-CR/non-PD' is preferred over 'stable disease' for non-target disease since SD is increasingly used as an endpoint for assessment of efficacy in some trials so to assign this category when no lesions

\*\*Only for non-randomized trials with response as primary endpoint.

\*\*\*In exceptional circumstances, unequivocal progression in non-target lesions may be accepted as disease progression.

can be measured is not advised

# 4.2.6 Progression-Free Survival

Progression free survival (PFS) is defined as the time from start of treatment (Cycle 1, Day 1) until the date of objective disease progression or death (by any cause in the absence of progression) regardless of whether the patient withdraws from therapy or receives another anti-cancer therapy before progression. Clinical deterioration in the absence of radiographic evidence is not considered progression for purposes of determining PFS. Subjects who die without a reported prior progression will be considered to have progressed on the date of their death. Subjects who did not progress or die will be censored on the date of their last evaluable tumor assessment. Subjects who did not have any on study tumor assessments and did not die will be censored on the date they were first treated. Subjects who started any palliative local therapy or subsequent anti-cancer therapy without a prior reported progression will be censored at the last evaluable tumor assessment prior to initiation of the palliative local therapy or subsequent anti-cancer therapy, whichever procedure occurred first.

The PFS time will always be derived based on scan/assessment dates not visit dates.

RECIST version 1.1 assessments/scans contributing towards a particular visit may be performed on different dates. The following rules will be applied:

- Date of progression will be determined based on the earliest of the dates of the component that triggered the progression
- When censoring a patient for PFS the patient will be censored at the latest of the dates contributing to a particular overall visit assessment.

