# 4.2.3.1 Efficacy Endpoints

In addition to a baseline scan, confirmatory scans will be obtained 4-6 weeks following initial documentation of objective response. Response and progression will be evaluated in this study using the new international criteria proposed by the revised Response Evaluation Criteria in Solid Tumors (RECIST) guideline (version 1.1)(Eisenhauer et al., 2009). Changes in the largest diameter (unidimensional measurement) of the tumor lesions and the shortest diameter in the case of malignant lymph nodes are used (Schwartz et al., 2009).

Patients who are found to have stable disease (SD), partial response (PR), or complete response (CR) will continue on study until evidence of disease progression, intolerance, or withdrawal from study. Response rate, overall survival, and progression-free survival will be determined. Subjects with progressive disease by RECIST 1.1 but without rapid clinical deterioration may continue to be treated at the discretion of the investigator.

The efficacy analysis will be based on the treated Population which includes all subjects who receive any dose of either investigational product. The following efficacy endpoints will be analyzed.

- Objective response is defined as confirmed CR or confirmed PR based on modified RECIST guidelines version 1.1. The ORR will be estimated by calculating the proportion of subjects who achieve OR; the 80% CI and 95% CI for the OR rate will be estimated using the exact binomial distribution.
- Disease control is defined as CR, PR, or SD based on RECIST guidelines version 1.1 with modifications. The disease control rate (DCR) will be estimated by the proportion of subjects who achieve DC, and its 80% CI and 95% CI will be estimated using the exact binomial distribution.

• Progression-free survival will be measured from the start of treatment with pembrolizumab and vorinostat until the documentation of disease progression or death due to any cause, whichever occurs first. For subjects who are alive and progression-free at the time of data cut-off for analysis, PFS will be censored at the last tumor assessment date. The Kaplan-Meier method (Kaplan and Meier, 1958) will be used to estimate the PFS curve and the PFS rate at time points of interest.

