- Duration of response is defined as the duration from the first documentation of OR to the first documented disease progression or death due to any cause, whichever occurs first. For subjects who are alive and progression-free at the time of the data cut-off for the analysis, DoR will be censored at the last tumor assessment date. The DoR will only be evaluated for the subgroup of subjects with an OR and will be calculated using the Kaplan-Meier method.
- Overall survival will be determined as the time from the start of treatment with pembrolizumab and vorinostat until death due to any cause. For subjects who are alive at the time of data cut-off, OS will be censored on the last date when subjects are known to be alive. The Kaplan-Meier method will be used to estimate the OS curve and the OS rate at time points of interest.

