### 4.2.7 Duration of Response

- Duration of overall response: The duration of overall response is measured from the time measurement criteria are met for CR or PR (whichever is first recorded) until the first date that recurrent or progressive disease is objectively documented (taking as reference for progressive disease the smallest measurements recorded since the treatment started). The duration of overall CR is measured from the time measurement criteria are first met for CR until the first date that progressive disease is objectively documented. If a patient does not progress following a response, then their duration of response will use the PFS censoring time.
- Duration of stable disease: Stable disease is measured from the start of the treatment until the criteria for progression are met, taking as reference the smallest measurements recorded since the treatment started, including the baseline measurements.

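### Section 4.2.6 both counts and censors PFS events after a new anti-cancer therapy, and nothing in the plan says which rule governs

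*Combined protocol and SAP*

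**What the plan says.** Three sentences in the opening paragraph of 4.2.6 matter here.

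- **Definition.** PFS runs from Cycle 1 Day 1 to objective progression or death, "regardless of whether the patient withdraws from therapy or receives another anti-cancer therapy before progression".
- **Death.** "Subjects who die without a reported prior progression will be considered to have progressed on the date of their death". No exception is made for patients who had other treatment in between.
- **Censoring.** "Subjects who started any palliative local therapy or subsequent anti-cancer therapy without a prior reported progression will be censored". The date used is that of the last evaluable scan before whichever of the two therapies came first.

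Section 4.2.3.1 holds a second PFS definition. For subjects who are "alive and progression-free at the time of data cut-off for analysis, PFS will be censored at the last tumor assessment date". It mentions neither new anti-cancer therapy nor palliative local therapy.

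Duration of response is also defined twice. Section 4.2.3.1 measures it "from the first documentation of OR to the first documented disease progression or death due to any cause, whichever occurs first", and for patients alive and progression-free at cut-off "DoR will be censored at the last tumor assessment date". Section 4.2.7 runs it to objectively documented recurrence or progression; if a responder does not progress, "then their duration of response will use the PFS censoring time".

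**The concern.** The definition sentence and the censoring sentence address the same patients, those who start another anti-cancer therapy before progression, and give them opposite event status. Two analysts who each follow 4.2.6 faithfully can produce different PFS times and event counts from one dataset.

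The situation can arise in practice. Section 4.2.6 does not accept clinical deterioration without radiographic evidence as progression, and 5.8 lists several reasons for stopping other than progression. Patients who stop for such reasons may start another treatment with no progression on record.

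PFS is part of the phase II primary hypothesis in 3.1. The trial is open label (5.2.3), so a rule picked at the time of analysis would be picked with outcomes visible.

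**Working it through.** The plan states no PFS sample size, event count or power, so there is no figure to reproduce. The check sets the sentences side by side.

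**Same patient, both rules.** Let L be the last evaluable scan before the new therapy, P a later objective progression and D the date of death. Times run from Cycle 1 Day 1.

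| Course, with no progression reported up to L | Definition and death sentences | Censoring sentence |
|---|---|---|
| New anti-cancer therapy, then death without reported progression | Event at D | Censored at L |
| New anti-cancer therapy, then objective progression | Event at P | Censored at L |
| Palliative local therapy, then death without reported progression | Event at D (death sentence) | Censored at L |
| Palliative local therapy, then objective progression | The override clause does not name local therapy | Censored at L |

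The first two rows contradict each other outright. For local therapy the conflict comes from the death sentence alone.

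**Search for a precedence rule.** Section 4.2.3.1 is silent on both therapies. Section 8 contains no PFS analysis, no split into primary and sensitivity analyses, and no statement ranking the rules.

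**What would be observed after a switch.** Sections 5.8 and 7.1.7.2 end disease-status follow-up when a new cancer treatment starts. Footnote d of the flow chart does not repeat that stop. Section 7.1.7.2.1 then moves the patient to telephone contact for survival every 12 weeks. Later progression would be largely unobserved, while deaths would still be recorded. The first row is therefore the one most likely to occur in the data.

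**Local therapy is a live case.** Section 5.5.2 may allow radiation to a symptomatic solitary lesion or the brain during treatment, and it prohibits nothing in post-treatment follow-up.

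**Duration of response.** Take a responder who switches and then dies without reported progression. Under the duration-of-response definition in 4.2.3.1 this is an event at death. Under 4.2.7 the PFS censoring time applies. That time is L under the censoring sentence; under the other reading the patient has a PFS event and no censoring time to carry over.

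**How many patients.** The documents give no switching rate. Assume that 5–20% switch before progression, with the 39 patients per arm of 8.2.6:

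- 39 × 0.05 = 1.95, about 2 per arm
- 39 × 0.20 = 7.8, about 8 per arm

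Only those who later progress or die change event status, so these are upper counts for each assumed rate.

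**Reach.** Section 8.2.5 names response rate as the primary endpoint. The two-stage rule, the posterior comparison and the simulated power in Section 8 all use response. Section 4.2.8 places the final response analysis at the time of PFS, but no PFS event count is set as a trigger, so the choice of rule does not move it.

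**The case against.** The strongest reply is that the censoring sentence is the specific, operational one and should be read as an exception to a general definition. The surrounding text fits it: the best-response cut-off in 4.2.8 stops at the same therapies, and 5.8, 7.1.7.2 and 7.1.7.2.1 end disease follow-up at new therapy. The part of the definition about withdrawing from therapy is not contradicted by anything.

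Much of this stands, and it is why censoring is the natural rule to keep. It does not remove the conflict. The definition is not a general rule silent on new therapy; it names that circumstance. If the censoring sentence governs, those words do nothing, and the death sentence still lacks an exception. Consistent follow-up is evidence of intent, not a stated precedence.

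A second reply is that PFS drives no decision in Section 8. That stands and limits the severity.

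A reader might go further and infer that one rule inflates PFS or favours an arm, or might try to put a figure on the shift in the median. The documents do not support this. They give neither a switching rate nor a risk after switching. If switching is unrelated to risk and leaves it unchanged, and progression is dated at scans as 4.2.6 requires, the censored and fully followed curves coincide. Otherwise the sign depends on whether risk rises or falls after the switch, and on whether only deaths are then seen. A modelled difference would mostly return its own assumptions.

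**Conclusion.** Wrong as written, minor severity. Section 4.2.6 assigns opposite event status to patients who start new anti-cancer therapy before progression and then progress or die. It does the same, through the death sentence only, to those who die after palliative local therapy. That conclusion rests on the text alone.

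The effect is confined to PFS and duration of response. A reader might infer that the phase II comparison itself is compromised because PFS stands in the primary hypothesis; the documents do not support that, since response rate is the named primary endpoint and the only quantity in the sample size, stopping and winner rules. The figure of about 2–8 patients per arm depends entirely on the assumed 5–20% and says nothing about the size or direction of any change in PFS.

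**What to change.** Before any PFS analysis, make one rule primary for both arms. Censoring at the last evaluable scan before new anti-cancer therapy fits the data collected. To adopt it:

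1. In the definition sentence of 4.2.6, delete the half of the clause about receiving another anti-cancer therapy and keep the half about withdrawing from therapy.
2. Limit the death sentence to patients who had not started such therapy.
3. State separately whether palliative local therapy censors and, if it does not, that later progression or death counts. The best-response cut-off in 4.2.8 already matches censoring for both therapies, so it needs a second look only if local therapy is treated differently.
4. Align the PFS and duration-of-response definitions in 4.2.3.1, and the duration rule in 4.2.7, with the choice.

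An analysis that counts events after a switch is optional as a sensitivity analysis. If run, it should say that progression after the switch is largely unobserved while deaths are still collected.

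The cost is protocol and SAP wording, plus at most that one extra analysis. No new data are needed.

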### 4.2.7 Duration of Response

- Duration of overall response: The duration of overall response is measured from the time measurement criteria are met for CR or PR (whichever is first recorded) until the first date that recurrent or progressive disease is objectively documented (taking as reference for progressive disease the smallest measurements recorded since the treatment started). The duration of overall CR is measured from the time measurement criteria are first met for CR until the first date that progressive disease is objectively documented. If a patient does not progress following a response, then their duration of response will use the PFS censoring time.
- Duration of stable disease: Stable disease is measured from the start of the treatment until the criteria for progression are met, taking as reference the smallest measurements recorded since the treatment started, including the baseline measurements.

# 4.2.8 Objective Response Rate

ORR is defined as the number of subjects whose best confirmed objective response (BOR) is a CR or PR, divided by the number of subjects who received at least one dose. BOR is defined as the best response designation, as determined by the RECIST v1.1, recorded between baseline and the date of objectively documented progression per RECIST 1.1 or the date of initiation of palliative local therapy or the date of initiation of subsequent anticancer therapy, whichever occurs first. For subjects without documented progression or palliative local therapy or subsequent anti-cancer therapy, all available response designations will contribute to the BOR determination. The final analysis of ORR will take place at the time of PFS.

#### 4.2.9 Overall Survival

OS is defined as the duration of time from the date for first treatment (Cycle 1 Day 1) to the date of death. A subject who has not died will be censored at last known date alive.

# 4.2.10 Missing Assessments and Not Evaluable Designation

When no imaging/measurement is done at all at a particular time point, the subject is not evaluable (NE) at that time point. If only a subset of lesion measurements can be made at an assessment, the case is also considered NE at that time point, unless a convincing argument can be made that the contribution of the individual missing lesion(s) would not have changed the assigned time-point response.

# 4.2.11 Treatment Beyond Progression

Accumulating evidence indicates a minority of subjects treated with immunotherapy may derive clinical benefit despite initial evidence of PD.

Subjects will be permitted to continue treatment beyond initial RECIST v1.1 defined PD as long as they meet the following criteria:

- Investigator-assessed clinical benefit and subject is tolerating study drug.
- No evidence of significant clinical decline.
- Subjects will be re-consented with an informed consent document describing any reasonably foreseeable risks or discomforts and other alternative treatment options. A follow-up scan should be performed within six 6 weeks +/- 7 days of original PD to determine whether there has been a decrease in the tumor size, or continued PD. The assessment of clinical benefit should be balanced by clinical judgment as to whether the subject is clinically deteriorating and unlikely to receive any benefit from continued treatment with Pembrolziumab ( + vorinostat for Arm B). If the investigator feels that the subject continues to achieve clinical benefit by continuing treatment, the subject should remain on the trial. The decision to continue treatment should be discussed with sponsor documented in the study records. \*\*For the subjects who continue study therapy beyond progression, further progression is defined as an additional 20% increase in tumor burden from time of initial

PD. This includes an increase in all target lesions and any new measurable lesions. Study therapy should be discontinued if further progression is documented. New lesions are considered measureable at the time of initial progression if the longest diameter is at least 10mm (except for pathological lymph nodes which must have a short axis of at least 15 mm). Any new lesion considered non-measureable at the time of initial progression may become measureable and therefore included in the tumor burden if the longest diameter increases to at least 10 mm (except for pathological lymph nodes which must have a short axis of at least 15 mm). The diameter(s) of any measurable new lesion(s) should be added to the target lesion sum of longest diameters in determining whether the criteria for further progression has been met.

